6.1.6 Pregnancy

Pregnancy in a study subject must be reported to AbbVie within 24 hours of the site becoming aware of the pregnancy. Subjects who become pregnant during the study must be discontinued from study drug (Section 5.4.1).

Information regarding a pregnancy occurrence in a study subject and the outcome of the pregnancy will be collected.

Pregnancy in a study subject is not considered an adverse event. The medical outcome for either mother or infant, meeting any serious criteria including an elective or spontaneous abortion, is considered a serious adverse event and must be reported to AbbVie within 24 hours of the site becoming aware of the event.

6.1.7 Cardiac Adjudication Committee

The independent external CAC will be adjudicating observed cardio- and cerebro-vascular events and will remain blinded to treatment allocation. The events that are adjudicated

and the adjudication process will be detailed in the Cardiac Adjudication Committee Charter. Dedicated eCRFs will be used for events of myocardial infarction-unstable angina, stroke-transient ischemic attack, and death. In addition, the site may be contacted for additional source documentation for relevant events.

6.1.8 Anaphylaxis Adjudication Committee

The independent external AAC will be adjudicating observed potential anaphylactic events and will remain blinded to treatment allocation. The events that are adjudicated and the adjudication process will be detailed in the Anaphylaxis Adjudication Committee Charter. A supplemental eCRF will be used to collect information pertinent to the events. In addition, the site may be contacted for additional source documentation for relevant events.

6.2 Product Complaint

6.2.1 Definition

A Product Complaint is any Complaint (see Section 6.0 for the definition) related to the biologic or drug component of the product.

For a product this may include, but is not limited to, damaged/broken product or packaging, product appearance whose color/markings do not match the labeling, labeling discrepancies/inadequacies in the labeling/instructions (example: printing illegible), missing components/product, or packaging issues.

Any information available to help in the determination of causality to the events outlined directly above should be captured.

6.2.2 Reporting

Product Complaints concerning the investigational product must be reported to the Sponsor within 24 hours of the study site's knowledge of the event via the Product Complaint form. Product Complaints occurring during the study will be followed-up to a

satisfactory conclusion. All follow-up information is to be reported to the Sponsor (or an authorized representative) and documented in source as required by the Sponsor. Product Complaints associated with AEs will be reported in the study summary. All other complaints will be monitored on an ongoing basis.

Product Complaints may require return of the product with the alleged complaint condition. In instances where a return is requested, every effort should be made by the Investigator to return the product within 30 days. If returns cannot be accommodated within 30 days, the site will need to provide justification and an estimated date of return.

The description of the complaint is important for AbbVie in order to enable AbbVie to investigate and determine if any corrective actions are required.

7.0 Protocol Deviations

AbbVie does not allow intentional/prospective deviations from the protocol unless when necessary to eliminate an immediate hazard to study subjects. The principal Investigator is responsible for complying with all protocol requirements, and applicable global and local laws regarding protocol deviations. If a protocol deviation occurs (or is identified, including those that may be due to the COVID-19 pandemic) after a subject has been enrolled, the principal Investigator is responsible for notifying IEC/IRB regulatory authorities (as applicable), and AbbVie.

Such contact must be made as soon as possible to permit a review by AbbVie to determine the impact of the deviation on the subject and/or the study.

In Japan, the Investigator will record all protocol deviations in the appropriate medical records at site.

8.0 Statistical Methods and Determination of Sample Size

8.1 Statistical and Analytical Plans

The objective of the statistical analyses is to evaluate the efficacy and safety of risankizumab versus placebo in subjects with moderately to severely active CD who had baseline eligibility SES-CD of ≥ 6 (≥ 4 for isolated ileal disease).

When all patients complete their Week 12/PD visit, the database will be locked and unblinded for the 12-week induction period. The planned analysis for the 12-week induction period will be performed. This is the only and final analysis for co-primary endpoints of the 12-week induction period. When all the patients who enter the induction Period 2 finish Week 24/PD visit, the database will be locked for the whole study and all the planned analyses for the induction Period 2 will be performed.

Complete, specific details of the statistical analyses will be described and fully documented in the study Statistical Analysis Plan (SAP). The SAP will be finalized prior to the study database lock.

The impact of missing data due to COVID-19 will be monitored and appropriate modifications to the analysis of primary and key secondary endpoints for handling such missing data will be reflected and incorporated in the final SAP.

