The IV risankizumab dose or matching IV placebo will be given at Weeks 12, 16, and 20. The SC risankizumab dose or matching SC placebo will be given at Weeks 12, and 20.

At Week 24, subjects who participated in the blinded Induction Period 2 will be reassessed and undergo a third endoscopy for evaluation of mucosal inflammation. Subjects who achieve clinical response at Week 24 may be eligible to enter Study M16-000. Subjects without clinical response at Week 24, as well as all subjects who terminate the study early (including subjects who are eligible for but do not participate in the blinded Induction Period 2), will be discontinued and have a follow-up call 140 days from the last dose of study drug to obtain information on any new and/or ongoing AEs.

Concomitant aminosalicylates, corticosteroids, immunomodulators (azathioprine [AZA], 6-mercaptopurine [6-MP], methotrexate [MTX]), and/or CD-related antibiotics

Subjects taking aminosalicylates, immunomodulators, and/or CD-related antibiotics at Baseline must continue their concomitant treatment for the duration of the study. Initiating and/or increasing doses of aminosalicylates, immunomodulators, and/or CD-related antibiotics during the study is prohibited. Decreasing doses of aminosalicylates, immunomodulators, and/or CD-related antibiotics is prohibited during the study, except in the event of moderate-to-severe treatment related toxicities and after discussion with the AbbVie Therapeutic Area Medical Director (TA MD). CD-related antibiotics may be discontinued in Induction Period 2 at the discretion of the Investigator.

Note: the duration of the study includes Induction Period 2.

Concomitant Corticosteroids

Subjects taking corticosteroids at Baseline must continue their concomitant treatment at the Baseline dose for the duration of the 12-week induction period. Initiation and/or increasing doses of systemic and/or CD related corticosteroids during the entire study is prohibited. Decreasing doses of corticosteroids is prohibited during the 12-week induction period, except in the event of moderate-to-severe treatment related toxicities and after discussion with the AbbVie Therapeutic Area Medical Director (TA MD).

Subjects who receive blinded therapy in Induction Period 2 during Weeks 12 to 24 will be allowed to taper their corticosteroids at the discretion of the Investigator. While stopping the taper is permitted, increasing doses above the Baseline dose is prohibited.

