6.1.4 Adverse Event Collection Period

All adverse events reported from the time of study drug administration until 140 days from the last dose of study drug have elapsed will be collected, whether solicited or spontaneously reported by the subject. In addition, serious adverse events and protocol-related nonserious adverse events will be collected from the time the subject signed the study-specific informed consent.

Adverse event information will be collected as shown in [Figure 2](#).

Figure 2. Adverse Event Collection

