8.1.7 Safety Analysis

Safety analyses will be carried out using the safety analysis sets, which includes all subjects who receive at least one dose of study drug. Incidence of AEs, including those related to study drug, changes in vital signs, physical examination results, and clinical laboratory values will be analyzed.

Adverse events will be coded using the Medical Dictionary for Regulatory Activities (MedDRA) dictionary. Treatment-emergent AEs are defined as AEs that began or worsened in severity after initiation of study drug and within 140 days after the last dose of the study drug. An overview of treatment-emergent AEs, including AEs leading to death and AEs leading to premature discontinuation (see details in the SAP), AEs by MedDRA preferred term and system organ class, AEs by maximum relationship to study drug, and AEs by maximum severity will be summarized by number and percentage.

Continuous laboratory and vital sign parameters will be summarized for each treatment group by visit. Treatment group differences between each of the risankizumab dosing groups and the placebo group for changes from Baseline may be analyzed using a one-way Analysis of Variance (ANOVA). Vital signs and laboratory data will be described by statistical characteristics and frequency of abnormal values. In addition, shift tables and listings will be provided for abnormal values, whereby the normal range of the analyzing laboratory will be used. Analysis details will be specified in the SAP.

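### The whole-study database lock at the last Week 24 visit comes before the 140-day safety window closes, so late-finishing subjects who do not roll over lose part of that window from the locked data

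*Protocol*

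**What the plan says.** Section 8.1 sets two locks. The first, after all Week 12/PD visits, serves the 12-week induction analysis. The second is described thus: "When all the patients who enter the induction Period 2 finish Week 24/PD visit, the database will be locked for the whole study", and all planned Induction Period 2 analyses are then run. The synopsis says the same.

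Dosing in Induction Period 2 is set in section 5.1: "The IV risankizumab dose or matching IV placebo will be given at Weeks 12, 16, and 20" and "The SC risankizumab dose or matching SC placebo will be given at Weeks 12, and 20". The last scheduled dose is therefore at Week 20 by either route.

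The safety window is set separately:
- Section 5.1: subjects without clinical response at Week 24 and subjects who stop early are to "have a follow-up call 140 days from the last dose of study drug to obtain information on any new and/or ongoing AEs". Section 5.4.1 describes a final visit at about that time for everyone not rolled over, and note c of Appendix C exempts only those who enter Study M16-000.
- Section 6.1.4: all AEs "reported from the time of study drug administration until 140 days from the last dose of study drug have elapsed will be collected".
- Section 8.1.7: treatment-emergent AEs are those that began or "worsened in severity after initiation of study drug and within 140 days after the last dose of the study drug". The synopsis adds that for subjects who enter Study M16-000 the window ends at their first dose there; section 8.1.7 omits this exception.

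Section 13.0 defines the end of study as the last subject's last visit.

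**The concern.** A lock for the whole study should contain the data that the planned tables need. The AE tables use a definition that reaches 140 days past the last dose, but the lock falls four weeks after the last scheduled dose of the last subject. The protocol provides no later lock, no lock limited to particular data, and no safety update. Taken literally, it closes the database before its own end of study.

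What is at stake is the final AE summary. Tables headed by the 140-day definition would contain subjects with shorter follow-up, and how short would depend on the calendar date of their Week 24 visit. Truncation can only remove events, so incidence could be understated. The subjects concerned are Week 24 non-responders, early leavers and responders who do not continue, so Study M16-000 will not pick up their later events. Evaluating the safety of re-induction is a stated purpose of Induction Period 2 (section 5.6.4).

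**Working it through.** **Inputs.** Last Induction Period 2 dose: Week 20 (5.1). Follow-up: 140 days / 7 = 20 weeks (5.1, 6.1.4, 8.1.7). Lock: last subject's Week 24/PD visit (8.1). Visit window: ±7 days (5.1). Last dose for a subject who does not enter Induction Period 2: Week 8 (5.1).

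**The plan's own figure.** Section 5.1 gives a maximum duration of 49 weeks: 35/7 + 12 + 12 + 140/7 = 5 + 12 + 12 + 20 = 49. This reproduces, and it shows that the protocol counts follow-up as part of the study. The sum starts the 140 days at Week 24, however. Counted from the last dose, as the same sentence says, it is 5 + 20 + 20 = 45 weeks.

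**Gap for the last subject.** The window closes at Week 20 + 20 = Week 40. Gap = 40 − 24 = 16 weeks = 112 days, and 112/140 = 80%. Only 4 of 20 post-dose weeks are in the database.

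With ±1 week on the Week 20 and Week 24 visits, the gap runs from (19 + 20) − 25 = 14 to (21 + 20) − 23 = 18 weeks. If the last subject instead leaves through a PD visit within 2 weeks of the last dose (5.4.1), at least 20 − 2 = 18 weeks remain.

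**Earlier completers.** A completer whose Week 24 visit is t weeks before the lock loses max(0, 16 − t) weeks: 16 at t = 0, 8 at t = 8, none from t = 16.

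**Subjects who stop after the Week 8 dose.** Their window closes at Week 8 + 20 = Week 28. One enrolled on the same day as the last Induction Period 2 subject is 28 − 24 = 4 weeks short at the lock.

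**Share of the group.** The protocol gives no accrual time, so this rests on an assumption: non-roll-over completers reach Week 24 uniformly over 2 to 3.5 years (104 to 182 weeks). For orientation only, the original protocol is dated February 2017 and the current synopsis September 2020.

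| Accrual | Affected | Mean loss if affected | Group follow-up lost |
|---|---|---|---|
| 104 weeks | 16/104 = 15.4% | 8 of 20 weeks (40%) | 15.4% × 0.40 = 6.2% |
| 182 weeks | 16/182 = 8.8% | 8 of 20 weeks (40%) | 8.8% × 0.40 = 3.5% |

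The mean loss is 16/2 = 8 weeks because t is uniform between 0 and 16.

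**The case against.** The strongest reply is that little is lost. Roll-over subjects have no 140-day contact. Most non-roll-over subjects will have completed theirs before the lock. AEs are still collected to 140 days, and SAEs still go to pharmacovigilance within 24 hours (6.1.5). Analysis details are left to the SAP, which could provide a later safety cut. The co-primary and ranked endpoints end at Week 12 and come from the earlier lock, and every Induction Period 2 group receives risankizumab, so the missing tail is largely uncontrolled follow-up.

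All of this stands as a limit on size. It does not remove the conflict: the protocol itself fixes the trigger and calls that lock the one for the whole study. An SAP that applied the 140-day definition in full would contradict that sentence, and one that kept to the sentence could not deliver the definition.

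Stronger readings are tempting but not supported:
- **That 80% of post-treatment safety follow-up is lost.** This is the figure for the last on-schedule completer only.
- **That the events go unrecorded.** Sections 5.1, 5.4.1 and 6.1.4 still require the contact and the collection. What is unsettled is which data cut feeds the final tables.
- **That those affected are the most exposed subjects.** Three 600 mg IV doses then two 180 mg SC doses total 3 × 600 + 2 × 180 = 2160 mg. A subject who stops at Week 12 after three 1200 mg doses has had 3600 mg, and a former placebo subject given three 1200 mg doses has also had 3600 mg. Only 1200 mg IV in both periods reaches 6 × 1200 = 7200 mg, and responders on that sequence who roll over have had the same.

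**Conclusion.** The point holds as an internal contradiction of limited size. The stated whole-study lock excludes part of the safety window for subjects who do not enter Study M16-000 and whose Week 24 visit falls within about 16 weeks of the lock, and for some late-enrolled subjects who stop after Week 8. It should be fixed, but it does not threaten the trial's main conclusions: type I error, power and the Week 12 and Week 24 efficacy analyses are unaffected.

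The 16-week gap rests on the protocol's schedule alone and takes the lock to coincide with the last Week 24 visit; any delay for data cleaning shortens it. The group-level shares rest on the uniform-accrual assumption; slower accrual makes them smaller, and a cluster of late enrolments makes them larger. The effect on AE incidence cannot be sized, because the protocol gives no event rates.

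**What to change.** In section 8.1 and the synopsis, rename the Week 24 event the Induction Period 2 lock. Calling it an efficacy lock would be too narrow, since all Induction Period 2 analyses, including safety, are run then. Add that the whole-study lock, or a pre-specified follow-up safety update, takes place after the last subject's 140-day contact or first M16-000 dose, and that the final AE tables come from that later cut. AE tables produced at the Induction Period 2 lock should state that follow-up is incomplete for some subjects.

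At the same time, carry the M16-000 exception from the synopsis into section 8.1.7, and reconcile the 49-week duration in section 5.1 with follow-up counted from the last dose.

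The cost is a change of wording and final safety tables about 16 weeks later. The Week 12 and Week 24 analyses keep their dates, and no additional data are collected.

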8.1.1 Datasets for Analysis

8.1.1.1 Intent-to-Treat Analysis Set

The intent-to-treat (ITT) analysis set includes all randomized subjects who received at least one dose of study drug. The primary population for efficacy analysis are the subjects in the intent-to-treat set who had baseline eligibility SES-CD of ≥ 6 (≥ 4 for isolated ileal disease). The ITT subjects will be analyzed as randomized.

8.1.1.2 Safety Analysis Set

The safety analysis set consists of all subjects who received at least one dose of the study drug. The safety set will be analyzed as treated, according to treatment the subject actually received. The safety set will be used for safety analysis.

8.1.2 Definition of Missing Data Imputation

Missing data will be imputed using one or more of the following methods:

Non-Responder Imputation (NRI): In NRI analyses, subjects who prematurely discontinue the study prior to efficacy assessment at Week 12 will be considered non-responders with respect to the efficacy endpoint.

Observed Cases (OC): The OC analysis will not impute values for missing evaluations, and thus a subject who does not have an evaluation on a scheduled visit will be excluded from the OC analysis for that visit.

8.1.3 Subject Disposition

The number and percentage of subjects who are enrolled, randomized and received at least one dose of study drug, and the number of subjects who prematurely discontinued and the reason for premature discontinuation will be summarized by treatment group. Premature discontinuation of study drug will be summarized for each treatment group, as well as for all subjects combined, with frequencies and percentages overall and by reason for discontinuation for all randomized subjects who received at least one dose of study drug. Subjects may have multiple reasons for prematurely discontinuing study drug, but will be counted no more than once for the total ("Any Reason").

8.1.4 Demographics and Baseline Characteristics

Demographics (where collection is allowed) and Baseline characteristics of the study subjects will be summarized using descriptive statistics. Summary statistics for continuous variables will include the number of observations, mean, standard deviation,

median, and range for each treatment group. For other categorical or discrete variables, frequencies and percentages will be computed in each category for each treatment group, as well as for all subjects combined.

8.1.5 Prior and Concomitant Medications

Prior therapy and medications will include all therapies and medications administered prior to the date of the first dose of study drug. Prior therapy and medication will be summarized for all randomized subjects. No statistical test will be performed.

Concomitant medications will be summarized for all randomized subjects. Concomitant medications will be summarized using the World Health Organization Drug Dictionary with frequencies and percentages for each treatment group. No statistical test will be performed.

8.1.6 Efficacy Analysis

8.1.6.1 Primary Efficacy Variables

The co-primary endpoints are the proportion of subjects who achieve CDAI clinical remission at Week 12 and proportion of subjects with endoscopic response at Week 12.

The comparisons between each risankizumab dose versus placebo for the primary efficacy variable will be performed using the Cochran-Mantel-Haenszel (CMH) test adjusted by number of prior biologics failed (0, 1, > 1) and steroid use at Baseline (yes, no). A multiple testing procedure will be used to provide strong control of the type 1 error rate at $\alpha = 0.05$ (2-sided) across analyses comparing each risankizumab dose level to placebo with respect to the co-primary endpoints, and ranked secondary endpoints. Specifically, testing will utilize a sequence of hypothesis testing for the co-primary endpoints followed by the ranked secondary endpoints, and will begin with testing each of the co-primary endpoints using α of 0.025 (2-sided) for each dose compared to placebo. If both co-primary endpoints achieve statistical significance within a dose level, continued testing will follow a pre-specified weight of α allocation between the single hypothesis within the family, as well as between the families of hypotheses across the doses. Details will be

provided in the Statistical Analysis Plan. A CMH based two-sided 95% confidence interval for the difference between treatment groups will be calculated. Subjects who discontinue prior to Week 12 for any reason will be considered as "not-achieved" for CDAI clinical remission and endoscopic response endpoints.

The analysis of co-primary efficacy endpoints will be performed in bio-IR and non-bio-IR population. Additional subgroup analyses will be outlined in the SAP. Sensitivity analyses for missing data handling using MI, PMM and OC will be performed for co-primary endpoints and details will be outlined in the SAP.

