5.2.1 Inclusion Criteria

1. Male or female aged ≥ 18 to ≤ 80 years, or minimum age of adult consent according to local regulations, at the Baseline Visit. Where locally permissible, subjects 16 to < 18 years of age who meet the definition of Tanner stage 5 for development (refer to [Appendix J](#)) at the Baseline Visit (sites will be notified when adolescents may enroll).
2. Confirmed diagnosis of CD for at least 3 months prior to Baseline. Appropriate documentation of biopsy results consistent with the diagnosis of CD, in the assessment of the Investigator, must be available.
3. Crohn's disease activity index (CDAI) score 220 – 450 at Baseline.
4. Endoscopic evidence of mucosal inflammation as documented by the SES-CD of ≥ 3 . All eligible scores exclude the presence of narrowing component and are confirmed by a central reader. (Once cap of no more than 85 subjects is reached, enrollment criterion will be an SES-CD of ≥ 6 for ileocolonic or colonic disease or SES-CD of ≥ 4 for isolated ileal disease.)
5. Average daily SF ≥ 4 and/or average daily AP score ≥ 2 at Baseline.
6. Demonstrated intolerance or inadequate response to one or more of the following categories of drugs: aminosalicylates, oral locally acting steroids, systemic steroids (prednisone or equivalent), immunomodulators, and/or biologic therapies
 - Demonstration of intolerance requires no minimum dose or duration of use (intolerance includes patients with a known TPMT genetic mutation or low activity).
 - Inadequate response is defined as outlined below:
 - Oral aminosalicylates (e.g., mesalamine, sulfasalazine, olsalazine, balsalazide):

- Signs and symptoms of persistently active disease, in the opinion of the Investigator, during a current or prior course of at least 4 weeks of treatment with 2.4 g/day mesalamine, 4 g/day sulfasalazine, 1 g/day olsalazine, or 6.75 g/day balsalazide,
- Oral locally acting steroids (e.g., budesonide, beclomethasone):
 - Signs and symptoms of persistently active disease in the opinion of the Investigator, during or after a course of at least 4 weeks of treatment with 9 mg/day budesonide or 5 mg/day beclomethasone,
 - or
 - Inability to taper oral budesonide to at or below 6 mg/day without recurrent active disease,
- IV or Oral systemic steroids (prednisone or equivalent):

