8.2 Determination of Sample Size

The co-primary endpoints are the proportion of subjects with CDAI clinical remission at Week 12 and proportion of subjects with endoscopic response at Week 12.

A total of approximately 855 subjects will be randomized into two risankizumab treatment groups and the placebo group in a 2:2:1 ratio (342 subjects for risankizumab 600 mg dose group, 342 subjects for risankizumab 1200 mg dose group, and 171 subjects for placebo group). Assuming the Week 12 CDAI clinical remission rate will be 37% for one of the risankizumab dose groups and 17% for the placebo group, a sample size of 342 subjects for each of the risankizumab dose groups and 171 for the placebo group will have 99% power to detect the treatment difference between the risankizumab dose groups and placebo in CDAI clinical remission rates at Week 12 using Fisher's exact test at alpha of 0.025 (two-sided). Assuming the Week 12 endoscopic response rate will be 25.5% for one of the risankizumab dose groups and 8% for the placebo group, this sample size will have 99% power to detect the treatment difference between the risankizumab dose groups and placebo in endoscopic response rates at Week 12 using a Fisher's exact test at alpha of 0.025 (two-sided).

In addition, with sample size of approximately 540 bio-IR subjects, this study will have approximately 92% power for the bio-IR population to detect the treatment difference between one of the risankizumab dose groups and placebo in CDAI clinical remission rates at Week 12 using Fisher's exact test at alpha of 0.025 (two-sided) for the bio-IR population, assuming the Week 12 CDAI clinical remission rate will be 34% for the risankizumab dose groups and 15% for the placebo group. Similarly, with sample size of approximately 315 non-bio-IR subjects, this study will have 70% power to detect the treatment difference between one of the risankizumab dose groups and placebo in CDAI clinical remission rates at Week 12 using Fisher's exact test at alpha of 0.025 (two-sided) for the non-bio-IR population, assuming the Week 12 CDAI clinical remission rate will be 42% for the risankizumab dose groups and 21% for the placebo group for non-bio-IR subjects.

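### The bio-IR and non-bio-IR analyses of CDAI remission could gain a few points of power, at almost no cost, by adjusting for Baseline CDAI

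*Protocol*

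**What the plan says.** References are to the current protocol (synopsis dated 01 September 2020).

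- **Test.** Section 8.1.6.1 compares each dose with placebo by a "Cochran-Mantel-Haenszel (CMH) test adjusted by number of prior biologics failed (0, 1, > 1) and steroid use at Baseline (yes, no". Baseline CDAI is not a factor.
- **Subgroups.** The same section states: "The analysis of co-primary efficacy endpoints will be performed in bio-IR and non-bio-IR population". It names no separate test for these analyses.
- **Endpoint and entry range.** Section 5.3.3 defines CDAI remission as CDAI below 150. Section 5.2.1 admits subjects by "Crohn's disease activity index (CDAI) score 220 – 450 at Baseline".
- **Availability.** Section 5.1 (Screening Period) requires CDAI to be calculated for every subject before randomization.
- **Non-bio-IR.** Under Section 5.1, subjects in this group who had a biologic before stopped it for reasons other than inadequate response or intolerance. Number of biologics failed is therefore 0 for all of them. (The synopsis labels the CMH factor as prior biologic use; this note follows Sections 8.1.6.1 and 8.3.)
- **Stated power.** Section 8.2: with about "315 non-bio-IR subjects, this study will have 70% power to detect the treatment difference", assuming "the Week 12 CDAI clinical remission rate will be 42% for the risankizumab dose groups and 21% for the placebo group for non-bio-IR subjects", "using Fisher's exact test at alpha of 0.025 (two-sided".

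**The concern.** A subject who enters at 220 needs a fall of just over 70 points to reach remission; one who enters at 450 needs just over 300. Where Week 12 CDAI tracks Baseline CDAI, part of the variation in remission can be predicted before treatment. A stratified test that leaves it out treats that variation as noise.

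This matters most in the non-bio-IR analysis. It is the smallest comparison and has the lowest power stated in Section 8.2, and one of the two CMH factors does not vary there. What is at stake is efficiency, meaning some power and some interval width. The validity of the planned test is not in question.

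**Working it through.** **Inputs from the protocol.** Allocation 2:2:1. Non-bio-IR: 315 × 2/5 = 126 per dose and 315 × 1/5 = 63 placebo, 42% v 21%. Bio-IR: 540 × 2/5 = 216 and 540 × 1/5 = 108, 34% v 15%. Full population: 342 v 171, 37% v 17%. Two-sided alpha 0.025.

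**Step 1: reproduce the stated figures.** Exact power of Fisher's test with 0.0125 in each tail is 70.5% in non-bio-IR (stated 70%), 92.5% in bio-IR (stated 92%) and 99.5% in the full population (stated 99%). The protocol's figures hold for the test it names.

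**Step 2: power of the planned type of test in non-bio-IR.** Without continuity correction:

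- pooled rate = (126 × 0.42 + 63 × 0.21)/189 = 66.15/189 = 0.35
- SE under the null = √[0.35 × 0.65 × (1/126 + 1/63)] = 0.0736
- SE under the alternative = √[0.42 × 0.58/126 + 0.21 × 0.79/63] = 0.0676
- power = Φ[(0.21 − 2.241 × 0.0736)/0.0676] = Φ(0.67), or 74.7%

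Simulated CMH stratified by steroid use (30% users assumed) also gives about 75%. Any gain should be counted from 75%, not from 70%.

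**Step 3: gain from Baseline CDAI in non-bio-IR.** The protocol gives no prognostic strength, so it has to be assumed. Marginal rates were held at 42% and 21%.

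*Model A:* Baseline CDAI uniform on 220 to 450, Week 12 CDAI correlated ρ with it, 6,000 trials per row.

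| ρ | CMH, steroid | CMH, steroid × CDAI tertile | Gain (points) |
|---|---|---|---|
| 0.2 | 75.0% | 75.1% | 0 |
| 0.3 | 73.9% | 75.3% | +1 |
| 0.4 | 74.4% | 77.8% | +3 |
| 0.5 | 75.2% | 81.4% | +6 |

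*Model B:* Baseline CDAI within 220 to 450 with SD 51.4; Week 12 CDAI is a linear function of it plus noise, cut at 150. The implied correlation is ρ = b × 51.4/√[(b × 51.4)² + s²], with slope b and residual SD s.

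| b, s | ρ | CMH, steroid | CMH + CDAI median split | Logistic + continuous CDAI |
|---|---|---|---|---|
| 0.4, 100 | 0.20 | 75.0% | 75.0% | 75.3% |
| 0.6, 100 | 0.29 | 74.8% | 76.0% | 76.4% |
| 0.8, 90 | 0.42 | 75.5% | 78.5% | 79.8% |
| 1.0, 90 | 0.50 | 74.4% | 79.2% | 81.2% |

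The two models agree: almost nothing at ρ = 0.2, and about 5 to 7 points at 0.5 depending on the method.

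*Model C:* strength set as the odds ratio for remission per SD higher Baseline CDAI. Going from CMH by steroid to logistic regression with CDAI, power moves from 74.7% to 76.7% at 0.6, from 74.6% to 78.4% at 0.5 and from 74.9% to 81.4% at 0.4. At 0.5 the gain is worth [(2.241 + 0.786)/(2.241 + 0.661)]² = 1.09, or roughly 9% more subjects.

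**Step 4: allow for discontinuation.** Section 8.1.6.1 counts discontinuers as failures whatever their Baseline CDAI, which weakens the association. With an assumed 10% dropout the gain is about 0 at ρ up to 0.2, +1 at 0.3, +3 at 0.4 and +3 to +4 at 0.5. A separate run with a truncated-normal baseline and 10% to 20% dropout gave about +1, +2 and +4 to +5 at 0.3, 0.4 and 0.5.

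**Step 5: downside.** If Baseline CDAI is not prognostic at all, power goes from 75.0% to 73.9% with tertile strata or 74.3% with logistic regression, a loss of about 1 point at most. Type I error stayed near 0.025: 0.025 v 0.023 at ρ = 0.5 (Model A), and 0.0246 (CMH), 0.0234 (with tertiles) and 0.0228 (logistic) at odds ratio 0.5 (Model C).

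**Step 6: the other populations.** In bio-IR, with 12 strata (biologics failed 1 or more than 1, steroid use, CDAI tertile) and 10% dropout, the gain is 0 to +2 points. In the full population, power moves from 99.6% to 99.7% at odds ratio 0.5.

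**The case against.** The strongest case is that nothing in the protocol is wrong. The test adjusts for both randomization factors that still vary in the primary population; the third, the SES-CD stratum, is constant there (Sections 8.1.1.1 and 8.3). That is a standard and valid choice, and this stands. The point is an improvement, not a correction.

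Three stronger readings are tempting, and the documents do not support them.

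- *The confirmatory co-primary test is underpowered for want of this covariate.* Its stated power is 99% and it gains essentially nothing. The benefit lies in subgroup analyses that Section 8.1.6.1 does not place in the alpha-controlled sequence.
- *The planned analysis has only 70% power in non-bio-IR.* Section 8.2 attaches the 70% to an unadjusted Fisher's exact test. About 5 points of the apparent shortfall come from that conservative sizing test.
- *The absolute cut makes Baseline CDAI prognostic by construction.* It does so only if Week 12 CDAI tracks Baseline CDAI. That is likely, but the protocol gives no figure, and at a correlation of 0.2 the gain is nil.

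It is also fair to say that the protocol does not state the test or factors for the subgroup analyses, and that such detail may sit in an SAP not at hand. That only steroid use remains as an adjustment is therefore an inference. It is the natural one, because Section 8.1.6.1 describes one test and no other, but the point is conditional on it.

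**Conclusion.** The planned CMH analysis is valid but leaves unused a complete pre-treatment value that is likely to predict the outcome. If it is carried into non-bio-IR, power is about 75%. Adjusting for Baseline CDAI would add about 0 to 6 points for an assumed correlation of 0.2 to 0.5, and nearer 0 to 4 after allowing for discontinuers counted as failures. The bio-IR gain is 0 to 2 points.

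The size rests on assumptions the protocol does not supply: the correlation, the Baseline CDAI distribution, 30% steroid users and the dropout rate. The gain is modest and does not turn the non-bio-IR comparison into a highly powered one. It is worth taking because it is nearly free and the possible loss is about 1 point.

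**What to change.** Leave the full-population co-primary test as stated. For CDAI remission in the bio-IR and non-bio-IR analyses, prespecify adjustment for Baseline CDAI in addition to the stated factors, by one of two routes chosen before unblinding:

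1. a Baseline CDAI tertile stratum in the CMH test and risk difference, with cut points fixed on blinded pooled data; or
2. logistic regression with continuous Baseline CDAI, testing the treatment coefficient (the quantity simulated above) and reporting a standardised risk difference.

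Keep the stated CMH as a sensitivity analysis.

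The cost is protocol or SAP wording; no new data are needed. Route 1 raises the strata from 2 to 6 in non-bio-IR (63/6, about 10 placebo subjects each) and from 4 to 12 in bio-IR (108/12 = 9 each), so some cells will be small. Route 2 avoids that. Either route loses up to about 1 point of power if Baseline CDAI proves not to be prognostic.
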